#### 8.2.1. NPANCOVA ANALYSIS

Ties will be handled using Efron's method [9].

The primary endpoint is time-to-event in nature and will be analysed using the nonparametric randomization-based covariate adjustment method of Saville and Koch (2013) [10] which is expanded to handle stratified randomisation by Hussey et al (2016) [11]. They refer to this method as NPANCOVA, and this naming will be preserved here.

NPANCOVA avoids the assumption of proportional hazards for each of the covariates. It does rely on the assumption of proportional hazards for the treatment effect as obtained from an unadjusted Cox proportional hazards model (with a single term for treatment and no covariates), but as is well known the p-value associated with this unadjusted estimate is comparable to the p-value obtained from the nonparametric log-rank test.

The method also does not make any assumptions about the relationship between the covariates and the outcome. The log hazard ratio can be viewed as a stratified population-averaged estimate.

#### Step One

The NPANCOVA method begins by fitting a stratified treatment-only Cox proportional hazards model. The model formula is:

$$\lambda(t; z_{hij}) = \lambda_{0h}(t) \times \exp(\beta z_{hij})$$
(1)

Where  $\lambda(t; z_{hij})$  is the hazard at time t for subject j in stratum h in treatment group i, where in this case  $h \in \{1,2,3,4\}, i \in \{1,2\}$ , and  $j \in \{1,2, ..., n_{hi}\}$ , where  $n_{hi}$  is the number of randomized subjects in treatment group i in that stratum.  $\lambda_{0h}(t)$  is the baseline hazard function for stratum h, and  $z_{hij}$  is the treatment group indicator for subject j in stratum h in treatment group i, which takes on a value 1 for the RD-X19 treatment group and 2 for the sham treatment group. In the next step, the Cox model from which DFBETA is obtained will have RD-X19 as the reference.

#### C Step Two

The vector, *r*, of DFBETA residuals is then calculated from fitting model (1) to all FAS subjects.

The DFBETA residual  $r_{ijh}$  concerns subject j in stratum h in treatment group i, and is equal to the absolute change in the estimated log hazard ratio,  $\hat{\beta}$ , resulting from model (1) but with subject j removed from the data set. It can be interpreted as a measure of the subject's influence.

The DFBETA residuals for all subjects are obtained from the stratified, treatment only Cox proportional hazards model. Define:

$$\boldsymbol{r}_{hi} = \left(r_{hi1}, r_{hi2}, r_{hi3}, \dots, r_{hin_{hi}}\right)^{T}$$

as the vector of DFBETA residuals for subjects in stratum h in treatment group i.

We then concatenate all the  $r_{hi}$ , resulting in a vector, r, of length n, where n is the number of randomized subjects in the study. In this study, because we have four strata and two treatment groups, so r will be constructed as:

# $\boldsymbol{r} = \left(\boldsymbol{r}_{11}^{T}, \boldsymbol{r}_{12}^{T}, \boldsymbol{r}_{21}^{T}, \boldsymbol{r}_{22}^{T}, \boldsymbol{r}_{31}^{T}, \boldsymbol{r}_{32}^{T}, \boldsymbol{r}_{41}^{T}, \boldsymbol{r}_{42}^{T}\right)^{T}$

Through the methods of Wei et al [12], as indicated by Saville & Koch (2013) [10] a robust estimate of the variance of  $\hat{\beta}$  (prior to adjusting for any covariates) is provided by the quantity  $\mathbf{r}^T \mathbf{r}$ .

#### Step Three

The method requires within-strata randomisation with regards to treatment allocation. In the present case there are four strata, corresponding to the crossing of two binary covariates: age (40-49 or  $\geq$  50) and baseline disease severity score (< 1.25 or  $\geq$  1.25). These will be coded as follows:

Stratum subscript (h)	Stratum
1	40-49, < 1.25
2	40-49, ≥ 1.25
3	≥ 50, < 1.25
4	≥ 50, ≥ 1.25

Furthermore, 1 will refer to the RD-X19 treatment group and 2 the Sham treatment group. So, for example, those in the RD-X19 treatment group within stratum  $\geq$  50, < 1.25 will have subscript '31' i.e., subject *j* in this stratum will have covariate vector  $\mathbf{x}_{31j}$ ; those in stratum 40-49, < 1.25 in the Sham treatment group will have subscript '12' i.e., subject *j* in this stratum will have covariate vector  $\mathbf{x}_{12j}$ .

NPANCOVA adjusts an initial estimate of the log hazard ratio (resulting from a treatment-only Cox proportional hazards model as in Step One) for covariates in a nonparametric manner. In this case, covariates are prognostic baseline covariates chosen to improve precision of the estimate of the log hazard ratio. Those covariates are:

- o Baseline Log10 nasopharyngeal viral load
- o Ethnicity
- Hours since onset of symptoms
- o Baseline Risk Factor Score (BRFS).

Further details on the definitions and numerical values for these baseline covariates and imputation of their missing values is described in Section 8.2.1.3. These covariates will be indexed as follows:

Index	Covariate
1	Baseline Log10 nasopharyngeal viral
	load
2	Ethnicity

3	Hours since onset of symptoms
4	Baseline Risk Factor Score

So, letting  $x_{hij}$  be the  $p \times 1$  vector of covariates (p is the number of covariates) for the *jth* individual in treatment group i from stratum h, in  $x_{hij}$  the first element will be their baseline Log10 nasopharyngeal viral load value, the second element will be their Ethnicity value, etc.

 $X_{hi}^{T} = (\mathbf{x}_{hi1}, \mathbf{x}_{hi2}, \mathbf{x}_{hi3}, \dots, \mathbf{x}_{hin_{hi}})$  is a  $p \times n_{hi}$  matrix containing the covariate information for the subjects in stratum h in treatment group i.

The  $p \times 1$  vector of covariate means in stratum h, treatment group i is given by:

$$\overline{\boldsymbol{x}}_{hi} = \frac{\sum_{j=1}^{n_{hi}} \boldsymbol{x}_{hij}}{n_{hi}}$$

and we define the  $n_{hi} \times p$  matrix:

$$C_{hi} = k \big( X_{hi} - \mathbf{1} \overline{\mathbf{x}}_{hi}^T \big)$$

where **1** is a column of 1s (with the same number of rows as  $X_{hi}$ ), meaning  $\mathbf{1}\overline{\mathbf{x}}_{hi}^{T}$  is a matrix of the same dimension as  $X_{hi}$ , where:

$$k = \frac{n_{h1}n_{h2}}{n_h W \sqrt{n_{hi}(n_{hi} - 1)}}$$

and

$$W = \sum_{h=1}^{4} \frac{n_{h1} n_{h2}}{n_h}$$

Where  $n_h$  is the number of subjects in stratum h and  $n_{h1}$  and  $n_{h2}$  are the numbers within stratum h in treatment groups 1 and 2, respectively.

The matrix  $C_{hi}$  can be interpreted as a scaled measure of the subject-wise deviations from the mean covariate values for stratum h in treatment group i.

An unbiased estimate for the covariance matrix of  $\overline{x}_{hi}$ , the vector of covariate means for those in treatment group *i* in stratum *h*, is then given by:

$$V_{\overline{x}_{hi}} = C_{hi}^T C_{hi}$$

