Currently, the predominant circulating strains – Omicron subvariants BA.4 and BA.5 – are highly communicable and are responsible for substantial morbidity and mortality, especially among individuals with risk factors for progression to severe COVID-19. What has not been well-characterized is the effect of COVID-19 risk factors on disease pathogenesis and outcomes among individuals who have upper airway COVID-19 at presentation to the health care system, or who never present to the health care system because they manage their COVID-19 at home. Multiple published

	Page 12 of 70
EmitBio Inc.	Version: 3.1
EB-P30-01	7 February 2024

sources of evidence are unequivocal in their finding that age is a critical risk factor for disease progression, the development of long COVID and the occurrence of post-COVID sequelae such as chronic pulmonary disease, including interstitial pulmonary fibrosis. EmitBio desires to initially target the use of RD-X19 to those who will most benefit from its use.

As shown in Table 1. below and as reported previously by others [14–17], among individuals meeting the FDA/NIH definition of mild COVID-19, age is a strong prognostic factor for time to COVID-19 symptom resolution, with subjects 40 years or older having substantially increased times to sustained symptom resolution.

Age	Sham median time to
category	sustained symptom resolution
category	(hours)
18-29	89.9
30-39	85.4
40-49	170.3
50-65	241.2

Table 1. Age is a prognostic factor for time to COVID-19 symptom resolution in sham treated subjects with mild COVID-19.

In view of the above findings, in this pivotal trial we plan to enroll subjects with mild COVID-19 who are age 40 or older, as described in detail below.

	Page 13 of 70
EmitBio Inc.	Version: 3.1
EB-P30-01	7 February 2024

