A subject is defined to have had subsequent disease progression if, after recording "SSSSS", they have "D" (disease progression) at even a single timepoint, or if pulmonary imaging demonstrates COVID-19 pneumonia

Note: A subject that has symptom recurrence and/or disease progression is still eligible to later have the event for the primary endpoint, if they subsequently have five consecutive assessments at which the signs and symptoms have resolved ("SSSSS"), but with no further subsequent rebound or subsequent disease progression during the subjects' remaining time on study.

Analyses of the Primary Endpoint

The method of primary analysis for the primary endpoint is nonparametric randomization-based covariate adjustment for time-to-event outcomes using Efron's method for handling ties, with stratification by the design's stratifications factors (age category [40-49, \geq 50] and baseline disease severity score [<1.25, \geq 1.25]), and with between one to four pre-specified (in the SAP) prognostic baseline covariates to improve precision of the estimate of the hazard ratio. This analysis will be based on the methods of Saville and Koch [20] as extended to stratified analyses by Hussey et al [21]. Testing for treatment will be carried out at the 5% two-sided significance level, and 95% two-sided confidence interval (CI) for the hazard ratio will also be derived. This primary analysis will be based on the FAS.

The non-parametric Kaplan-Meier method will also be used for the FAS to estimate the survival curves, within the plot of which the number of subjects at risk will also be displayed. The median survival time will be estimated for each treatment group, together with its 95% CI using the Brookmeyer & Crowley method [19]. Estimates of the 25th and 75th percentiles will also be derived together with their corresponding 95% CIs.

A secondary analysis will be carried out on the FAS for the primary endpoint based on a Cox Proportional Hazards model, using Efron's method for handling ties, including the same stratification factors and covariates as included in the primary analysis. In the analyses described above the following rules for event times and censoring will be implemented:

- (i) Subjects that are hospitalized will be censored at 360 hours (which corresponds to the end of the time window for the Day 14 visit) and this rule takes precedence over all other rules;

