#### **3.3.** DETERMINATION OF SAMPLE SIZE

The sample size was based on the primary end point of time to sustained symptom resolution. In the EB-P20-01 trial, for subjects aged 40-years-old or over with mild disease (based on the NIH and FDA definition of mild COVID-19), the hazard ratio for this endpoint in

<sup>1 The COVID-19 Composite Severity Score at baseline is defined as the sum of the eight individual COVID-19 symptom severity scores divided by eight.

the full analysis set (FAS) was 0.62. Assuming an overall (one-sided) type 1 error of 0.025, a total of 228 events for the primary endpoint gives 95% power for a hazard ratio of 0.62 and also gives 90% power for a hazard ratio of 0.65, as well as 80% power for a hazard ratio of 0.69.

A total of 326 subjects will be initially randomized 1:1 (to RD-X19 and Sham) which will result in approximately 228 events assuming that 90% of RD-X19 subjects and 50% of Sham subjects will have the event.

A blinded sample size review will be carried out by an independent statistician based on the first 164 randomized subjects, with the objective of seeing whether the sample size needs to be increased. See Section 8.1 for details.

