# 7.6. BASELINE COVID-19-RELATED INFORMATION AND OTHER BACKGROUND CHARACTERISTICS

The following variables will be summarised in tables for the FAS.

- Result of baseline SARS-Cov-2 antigen test (positive, negative, inconclusive)
- SARS-Cov-2 antigen test type (Flowflex, BinaxNOW)
- o Result of flu A rapid antigen test (positive, negative, invalid)
- Result of flu B rapid antigen test (positive, negative, invalid)
- Randomization Stratum (age 40-49, Disease Severity Score < 1.25; age 40-49, Disease Severity Score ≥ 1.25; age ≥50, Disease Severity Score < 1.25; age ≥50, Disease Severity Score ≥ 1.25)

- Total baseline disease severity score (continuous variable)
- Total baseline disease severity score (<1.0,  $\geq$ 1.0-<1.25,  $\geq$ 1.25-<1.75,  $\geq$ 1.75)
- Baseline individual self-assessed symptom scores:

- Cough (0,1,2,3)
- Sore throat (0,1,2,3)
- Nasal congestion (0,1,2,3)
- Headache (0,1,2,3)
- Chills or sweats (0,1,2,3)
- Myalgia (0,1,2,3)
- Fatigue (0,1,2,3)
- Nausea, with or without vomiting (0,1,2,3)
- Loss of taste (yes, no)
- Loss of smell (yes, no)
- Baseline oral temperature (continuous variable)
- o Baseline oral temperature (<100.5, ≥100.5 °F)
- Baseline heart rate beats/min (continuous variable)
- Baseline heart rate (<70, ≥70-<80, ≥80-<90, ≥90)

- Systolic blood pressure (mmHg)
- Diastolic blood pressure (mmHg)
- Oxygen saturation at rest (%)
- Respiratory rate at rest (continuous variable)
- o Respiratory rate at rest (<20, ≥20 breaths/min)
- Oxygen saturation from Dyspnea on exertion assessment (%)
- Respiratory rate from Dyspnea on exertion assessment (continuous variable)
- Respiratory rate ≥20 and Oxygen saturation <96% from Dyspnea on exertion assessment (yes, no)
- Hours at screening since onset of first COVID-19 sign or symptoms (continuous variable)
- Hours at screening since onset of first COVID-19 sign or symptoms ( $\leq 24$ ,  $>24-\leq 48$ ,  $>48-\leq 72$ , >72)
- Baseline Risk Factor Score (as defined in Section 8.2.1.3)
- Baseline Log10 Nasopharyngeal Viral Load category (Not Detected or Below LLOQ; Above ULOQ; Numerical value between LLOQ and ULOQ, missing)
- Baseline Log10 Nasopharyngeal Viral Load (summary statistics [copies/mL] for numerical value between LLOQ and ULOQ)

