#### 8.2.1.1. Hypothesis Testing

The test statistic will be

$$Z = \frac{\hat{b}_{,}}{\sqrt{\nu_b}} \tag{4}$$

which under  $H_0$  has an asymptotic N(0, 1) distribution.

A test will be carried out at the 5% two-sided significance level with the following hypotheses:

$$H_0:\beta = 0$$
$$H_1:\beta \neq 0$$

and the p-value reported.

Here only a p-value favoring the RD-X19 treatment group will be flagged as statistically significant. This p-value corresponds to the primary analysis of the primary endpoint.

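### The primary NPANCOVA uses baseline severity only through one cut at 1.25, and age only through a cut at 50 plus one risk-score point at 65; adding both continuous values might buy a little precision.

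*SAP*

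**What the plan says.** Protocol 9.4.1 specifies nonparametric randomization-based covariate adjustment, stratified by age (40-49, 50 or older) and baseline severity score (below 1.25, 1.25 or above), "with between one to four pre-specified (in the SAP) prognostic baseline covariates". SAP 8.2.1, Step Three, uses all four places: log10 nasopharyngeal viral load, ethnicity, hours since onset and BRFS. It explains that the "covariates are prognostic baseline covariates chosen to improve precision of the estimate of the log hazard ratio".

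The secondary Cox model (SAP 8.2.3) and the key secondary analyses (SAP 8.3.2) reuse the same strata and covariates. Under SAP 8.2.1.3, age 65 or older adds one point to BRFS, a capped composite of 12 factors.

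Both omitted values are available. SAP 7.5 summarises age as continuous. SAP 7.6 summarises the severity score as continuous and also in four bands. On prognosis, Protocol 4.1 states that "age is a strong prognostic factor for time to COVID-19 symptom resolution" and gives sham medians by age band in Table 1.

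**The concern.** The severity score is the mean of the eight symptom grades (Protocol 4.3), and those same eight symptoms must all fall to 0 or 1 for the primary event. It is in effect a baseline measure of the outcome. Inclusion criterion 3 admits one moderate symptom plus fever, a score of 2/8 = 0.25, and the maximum is 24/8 = 3.0. The two strata therefore span 0.25-1.125 and 1.25-3.0.

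For age, everyone from 50 upwards shares one band with no upper limit, and the BRFS point does not separate 50 from 64 or 66 from 80.

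Stratification removes differences between bands. Any prognostic information inside a band is left in the error. What is at stake is the width of the interval for the primary and key secondary hazard ratios, not their validity.

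**Working it through.** **1. The plan's own figure.** SAP 3.3 assumes one-sided 0.025 and 228 events, and claims 95% power at a hazard ratio of 0.62, with "90% power for a hazard ratio of 0.65, as well as 80% power for a hazard ratio of 0.69". Schoenfeld's formula gives power = Φ(½·√228·|ln HR| − 1.96), where ½·√228 = 7.550:

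- HR 0.62: 7.550 × 0.478 − 1.96 = 1.649, so 95.0%
- HR 0.65: 7.550 × 0.431 − 1.96 = 1.292, so 90.2%
- HR 0.69: 7.550 × 0.371 − 1.96 = 0.842, so 80.0%

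Expected events are 163 × 0.90 + 163 × 0.50 = 228.2. All figures reproduce with no allowance for covariate adjustment, so nothing promised depends on the covariate list.

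**2. What a variance reduction is worth.** If the two added values cut the variance by a further fraction R², effective events are 228/(1 − R²) and interval width on the log scale scales by √(1 − R²).

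| R² | Effective events | Width ratio | Power, HR 0.65 | Power, HR 0.69 |
|---|---|---|---|---|
| 0 | 228.0 | 1.000 | 90.2% | 80.0% |
| 2% | 232.7 | 0.990 | 90.8% | 80.8% |
| 5% | 240.0 | 0.975 | 91.6% | 82.0% |
| 8% | 247.8 | 0.959 | 92.4% | 83.2% |

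**3. How large R² might be.** The documents give no within-stratum effects, so these are assumptions. For age, Table 1 gives 170.3 h (40-49) and 241.2 h (50-65). With exponential times and band midpoints 44.5 and 57.5, the slope is ln(241.2/170.3)/13 = 0.348/13 = 0.027 log-hazard per year. For severity, 0, 0.2 and 0.4 log-hazard per SD were tried.

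The SAP's stratified NPANCOVA was simulated with 326 subjects and 1,500 runs per scenario, comparing the four SAP covariates with those four plus continuous age and severity. Further assumptions: severity mean 1.35 and SD 0.42, sham median about 200 h, about 7% early censoring, modest effects of viral load and BRFS, and untied event times.

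| Age per year; severity per SD | True HR | Variance ratio, estimated | Variance ratio, empirical | Power, four to six |
|---|---|---|---|---|
| 0; 0 | 0.69 | 0.994 | 1.006 | 81.1% to 81.0% |
| 0; 0 | 0.65 | 0.993 | 1.015 | 91.1% to 90.9% |
| 0.027; 0 | 0.69 | 0.979 | 0.980 | 78.8% to 79.2% |
| 0.027; 0 | 0.65 | 0.979 | 0.991 | 90.8% to 91.6% |
| 0.027; 0.2 | 0.69 | 0.970 | 0.967 | 75.8% to 76.9% |
| 0.027; 0.2 | 0.65 | 0.970 | 0.975 | 88.5% to 90.3% |
| 0.027; 0.4 | 0.69 | 0.946 | 0.961 | 77.3% to 80.4% |
| 0.027; 0.4 | 0.65 | 0.946 | 0.962 | 86.6% to 88.6% |
| 0.05; 0.4 | 0.69 | 0.926 | 0.927 | 75.8% to 78.5% |
| 0.05; 0.4 | 0.65 | 0.925 | 0.930 | 85.0% to 87.9% |

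The Monte Carlo standard error of each power is about 1 point. A 7% reduction equals 228/0.93 = 245.2 effective events, about 17 extra, and an interval narrower by 1 − √0.93 = 3.6%.

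**4. Type I error.** With a true hazard ratio of 1, one-sided rejection was 3.3% with four and 3.3% with six covariates (age 0.027, severity 0.2), and 2.6% against 2.7% (no effects). The Monte Carlo standard error is about 0.4 points. The 3.3% is about two standard errors above 2.5%, but the analysis without covariates gave 3.1% in the same runs, so the excess does not come from the added terms.

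**The case against.** Several points on the other side stand.

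- A reader might infer that age is used only as a two-level stratum. It is not: the BRFS point at 65 is a second route, and other BRFS conditions may carry some age information.
- For the enrolled ages, Table 1 has two rows, and the cut at 50 falls exactly between them. The documented gradient is already used. The table shows nothing within a band, and its two youngest rows do not rise (89.9 h, then 85.4 h), so a straight line in age is an assumption.
- A reader might infer that two more covariates must narrow the interval. The SAP's variance formula (Step Five) subtracts a non-negative term, so the estimated variance cannot rise when covariates are added. With no within-stratum effect it fell by under 1%, while the empirical variance did not fall. Part of any estimated gain is therefore mechanical.
- A reader might infer that ethnicity should give up its place, because the documents show no prognostic data for it. They show none for the severity score either, so they cannot support that exchange.

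What remains is narrower. The severity score is built from the endpoint's own symptoms and is cut once, and both continuous values are already in hand. The subgroup hazard ratios by age and severity in SAP 8.2.6 do not recover precision for the primary estimate.

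**Conclusion.** The omission is real and its consequence is small. It is an efficiency choice within a valid, pre-specified analysis. Adding both values would be expected to lower the variance of the log hazard ratio by about 0-7%, or 0-4% in interval width and roughly 0-3 points of power. The middle scenarios give about 2-5% of variance.

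The range depends on assumed within-stratum effects and distributions, and the gain is nil if neither value is prognostic within strata. The documents do not support reading this as an underpowered design, a biased estimate or a type I error problem: 228 events and 326 subjects stand as calculated.

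**What to change.** Before database lock and unblinding:

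- Keep the four strata and the four existing covariates, including ethnicity.
- Add continuous baseline severity score and continuous age to the list in SAP 8.2.1, Step Three, and define them in 8.2.1.3. Carry them through to the key secondary NPANCOVA and the Cox models. The Cox hazard ratio is conditional on its covariates, so its target shifts slightly.
- In Protocol 9.4.1, change the limit from four to six, both for the primary endpoint and where the key secondary endpoint repeats it.
- Update the covariate index in Step Three, the vector lengths in Step Four (5 to 7 and 4 to 6) and the degrees of freedom of Q0 in SAP 8.2.1.4 (4 to 6).

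No new data are needed: both values are required for stratification at randomization. SAP 2.1 allows amendments before database lock. The main cost is the protocol amendment, which needs IRB approval before it is implemented (Protocol 10.1). If the sponsor judges that too much for a gain that may be nil, leaving the list as it is remains defensible.

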#### Step Four

We then define:

$$\boldsymbol{f} = \left(\hat{\boldsymbol{\beta}}, \overline{\boldsymbol{g}}^T\right)^T$$

as a row vector of length 5. This is the concatenation of the estimate for  $\beta$  (a scalar) and  $\overline{g}$  (which has length 4), where  $\overline{g} = \overline{x}_1 - \overline{x}_2$  is the (column) vector of weighted differences in covariate means between treatment groups, where

$$\overline{x}_{i} = \sum_{h=1}^{4} \frac{n_{h1} n_{h2} \overline{x}_{hi}}{n_{h} W}$$

A consistent estimate of f's covariance matrix is then given by:

$$V_{f} = \begin{bmatrix} \mathbf{r}^{T}\mathbf{r} & \sum_{h=1}^{4} (\mathbf{r}_{h1}^{T}C_{h1} - \mathbf{r}_{h2}^{T}C_{h2}) \\ \sum_{h=1}^{4} (C_{h1}^{T}\mathbf{r}_{h1} - C_{h2}^{T}\mathbf{r}_{h2}) & \sum_{h=1}^{4} \sum_{i=1}^{2} C_{hi}^{T}C_{hi} \end{bmatrix}$$

This is written more succinctly as:

$$V_f = \begin{bmatrix} \nu_{\widehat{\beta}} & V_{\widehat{\beta}\overline{g}}^T \\ V_{\widehat{\beta}\overline{g}} & V_{\overline{g}} \end{bmatrix}$$

As described in step 2 the quantity  $\mathbf{r}^T \mathbf{r} (= v_{\hat{\beta}})$  is a robust estimate of the variance of the estimator  $\hat{\beta}$  (prior to adjusting for any covariates).

The quantity  $V_{\hat{\beta}\overline{g}}$  provides an estimate of the covariance matrix for  $\hat{\beta}$  and  $(\overline{x}_1 - \overline{x}_2)$ .

The quantity  $V_{\bar{g}}$  provides an estimate of the covariance matrix for  $(\bar{x}_1 - \bar{x}_2)$ . This is an unbiased estimate under the assumption that the subjects are a simple random sample from a stratified population.

